6. HUMAN SUBJECTS PROTECTION

A. Potential Risks and Discomforts

Injury, Pain, or Fatigue: During neuromuscular testing, the primary risks are related to potential injury from the measurement of isokinetic leg strength. Participants may also be at risk of injury from a fall or improper landing during the drop vertical jump task (DVJ). Although the risk of injury during testing is real, ongoing studies utilizing these testing procedures in our laboratory have occurred over the past 7 years resulting in over 2000 subjects being tested. During this time, no injuries have occurred as a result of these procedures. Maximal effort will be requested during these measurements but participants will be instructed that they are free to stop if they experience too much discomfort. Rest breaks between measures will be allowed. We have completed neuromuscular assessment of over 40 adolescents with JFM as part of our preliminary work. Of these, 2 patients declined the drop vertical jump at initial testing, but were able to successfully complete the task after treatment. There were no injuries or adverse effects of the testing. Neuromuscular and aerobic training. Our pilot studies have shown that participants commonly report temporary increases in muscle soreness or fatigue when they initiate new exercise and this is to be expected. The PI, study physicians as well as our clinical physical therapists in the Rheumatology and Pain Clinics, all of whom have extensive experience treating adolescents with JFM, have reviewed and approved the neuromuscular and aerobic training protocol and provided their input to ensure that it is safe for use in this population.

Emotional Distress: Asking the adolescent participants to complete self-report measures about their symptoms, physical and psychological functioning typically does not result in distress. However, given the risk of elevated depressive symptoms in some JFM subjects, some responses on the depression measure may reveal depressive affect and/or suicidal thoughts. The CBT intervention used in this study has been well-tested in past studies and has not been associated with any adverse effects.

Confidentiality: There is a minimal risk that the data collected for each subject may be viewed by individuals outside the research team. The group-based treatment also presents a small risk to confidentiality if participants share personal information outside of the group sessions. Remote delivery via video-format also may pose some concerns about confidentiality if participants are not in a private location.

Note: Due to the COVID-19 pandemic and ongoing risk for virus transmission, we are cognizant that special safety precautions will be necessary for any in-person components of the study assessments and remote delivery of interventions.

B. Adequacy of Protection Against Risks

Injury, Pain, or Fatigue: The minimal risk of injury involved in neuromuscular testing will be further reduced by utilizing trained exercise physiologists supervised by site co-I's who are experts in exercise science research and an active warm-up and stretching period prior to the tests. In the unlikely event of an injury during the testing, a physician will be on site to supervise and take appropriate action. Designated lab space and exam rooms will be used to protect each subject's individual privacy throughout the testing procedures. Exercise difficulty for both the FIT

and GAE treatment protocols can be modified to the participants' abilities to minimize soreness and fatigue. Participants will also be allowed to take rest breaks during sessions. A study physician will be available at each site throughout the study to respond to any reports of JFM symptom flares or adverse events requiring medical attention, e.g., reports of severe pain beyond the expected muscle soreness related to initiating a new neuromuscular or graded aerobic exercise.

Emotional Distress/Suicidal Ideation: In the event that a participant reveals severe depressive symptoms or suicidal ideation (e.g. on the Children's Depression Inventory), a licensed psychologist co-I at the site will be immediately notified. A risk assessment, including detailed information about suicidal ideation, intent and/or plans, access to means to hurt themselves, major stresses, availability of social supports, access to treatment, and plans for safety will be discussed in detail with the patient and their parent. The assessment will be conducted by a PhD level psychologist. If the CDI is administered remotely (via video platform) due to pandemic restrictions, the site psychologist or institutional safety hotline mental health worker will be available to join the video call for further assessment. A referral to the ER (if necessary), and/or a referral to the Psychiatry Division or outpatient Psychology clinic, as appropriate, will be made. All actions taken will be documented in the participant's confidential folder and documented on an AE form. The cognitive-behavioral component of FIT Teens will be delivered by a trained licensed psychologist or postdoctoral fellow. Our extensive experience using CBT for JFM over the past 12 years indicates that participants have no difficulty with coping skills training, and no adverse effects related to CBT have occurred.

Confidentiality: All study staff are trained and certified in human subjects' protections including protection of confidentiality. Confidentiality will be maintained through the use of subject identification numbers on all case report forms. All consent forms, contact information and identifying data will be stored in a secure location within the PI's research lab on a passwordprotected computer. The primary study database will use the Medi-data Rave[®] platform which is the industry standard clinical trials software and will be customized to this study. This platform follows all the most updated good clinical practice guidelines for protecting subject information. All study data in the trial database will be entered with a Subject ID number only. The subject codebook and randomization schedule will be held confidentially by the study biostatistician ([name]) and the Regulatory Manager and will not be released until the data is locked down for analysis. Site coordinators will upload the video recordings on a restricted access server managed by the Clinical Coordinating Center. Site investigators will not have access to these videos nor will videos be linked to study data or a participant's PHI. Videorecordings of the sessions will be destroyed every six months, once they have been reviewed and rated. Before they begin the groupbased sessions, adolescents and parents will be informed about the importance of confidentiality and will sign a confidentiality contract which affirms that they will not share any personal or health information about other study participants outside of the study group (including on any social networking sites).

Note: for the duration of the COVID-19 pandemic, group-based in-person sessions will be replaced by remote sessions as described. Assessments will be minimized to brief in-person study visits (with most outcome measures collected electronically via REDCap surveys) and only include procedures allowable by each participating site's institutional policies. At the beginning of each treatment session, a "safety check" will be performed which will include ensuring that participants

are in a private location.

C. Informed Consent

The parent/legal guardian of each patient will provide written informed consent and the adolescent will provide written assent with the option of obtaining consent on an IRB approved paper consent, or via REDCap e-Consent using a computer, electronic tablet, or smart phone. When e-Consent is used, consent and/or assent will be collected by a typed signature or by obtaining the participant and parent's electronic signature using your finger, a mouse, or a stylus, depending on the resources available to the family. Once the e-Consent form is signed, the parent or legal guardian will be able to download a PDF version and/or receive an e-mail with a PDF attachment of the signed consent form. This will all be conducted before any study measures and interventions are undertaken. If the adolescent turns 18 in the course of the trial, they will be re-consented using an adult Consent Form. The parent of each participant will be asked to voluntarily complete a brief survey about the child's family history of pain. A waiver of documentation of consent is included at the top of the survey form.

In instances where it is necessary to consent a parent/legal guardian and child remotely using a paper form, the child and parent/legal guardian will be provided with copies of the IRB approved consent and assent (if applicable) to review prior to the call. Both the child and parent must be present remotely to participate in the remote consenting process. Study staff will review the consent (and assent, if applicable) documents with the family and provide time for the parent and child to ask questions and receive answers. The parent and child will sign and date the consent document(s) during the call. A copy of the entire consent (and assent if applicable) documents must be returned to study staff (either electronically, digitally, or via postal mail). The consentee will sign and date the documents using the same date of the call. Documentation that the consent was obtained remotely will occur on the informed consent/assent and the informed consent process note.

D. Participant Compensation

Participants will be reimbursed \$15 for transportation/mileage/effort for each study visit (participants residing greater than 25 miles from the treatment location will receive \$25 if they need to travel to the site for an in-person visit) and \$40 for each assessment. Those in the FIT group will receive a BOSU Balance Training Ball to facilitate exercise training at home. The CBT group will receive a gift basket of relaxation CDs/software, squishy stress balls etc. to facilitate use of relaxation and distraction strategies at home. The GAE group will receive a user-friendly activity monitor and heart-rate monitor to facilitate participation in aerobic activity.

E. Potential Benefits of the Proposed Research to Subjects and Others

Based upon our prior work with CBT and exercise interventions, we expect that all adolescents (CBT, FIT, and GAE) will experience direct benefit including better ability to cope with their pain, as well as improved mood and functioning. We have published a rigorous randomized clinical trial showing the benefits of CBT in reducing disability and mood difficulties in JFM. The enhanced protocol of CBT integrated with neuromuscular exercise training (FIT Teens) has been piloted by our team and shown to be a safe and highly engaging way to improve adolescents' ability and confidence in exercise by teaching them proper body biomechanics and fundamental movement skills. FIT Teens provides both the psychological coping skills and the foundation for safe exercise. Graded aerobic exercise has also been found to be feasible, safe and beneficial for

adolescents with JFM. If successful, this line of research has the potential to significantly impact clinical care for all adolescents suffering from JFM and improve their physical and emotional health outcomes.

F. Importance of Knowledge to be Gained

JFM is a chronic condition with no cure, and for which pharmacologic options show limited benefit. The knowledge gained in this study has a very high potential to improve the physical and emotional health of adolescents with juvenile fibromyalgia by integrating a self-management intervention into usual medical care. The new FIT Teens intervention goes beyond CBT techniques alone by combining CBT with neuromuscular training to improve fitness and physical function and reduce pain in adolescents with JFM. In this RCT, we will test if the combined effects of the FIT intervention are more powerful than CBT alone or a traditional exercise-only program (GAE).

G. Risk Benefit Analysis

There is minimal risk associated with participation in this study. The benefits to research participants include receiving an established evidence-based CBT intervention (in 2 of 3 groups) which is known to reduce disability and improve mood. Exercise interventions (neuromuscular training and aerobic exercise) have also shown early evidence of increasing strength, providing greater confidence in movement and improving daily functioning. Meeting and receiving support from other adolescent patients with JFM and obtaining more information about their pain condition have been uniformly reported as being highly beneficial by both participants and their parents. Potential risks for injury during exercise testing are very small. Although there is some risk for exercise induced/delayed onset muscle soreness which may be temporarily uncomfortable for some of the participants, the benefits of increased fitness, strength and longer-term pain reduction outweigh this risk. Information obtained from this relatively low-risk study will be extremely valuable to establishing the evidence for behavioral and exercise-based interventions for the treatment of adolescent JFM patients and potentially impact the clinical care for adolescents with this chronically painful condition.

7. STUDY TIMELINE

The revised timeline was approved by the Sponsor and DSMB due to delays caused by the pandemic.

	Yea	r 1			Year 2	Year 3	Year 4	Year 5	Year 6	Year 7
	Q1	Q2	Q3	Q4						
Screening patients										
Enrollment and					N - 105	N = 210			N-215	
Treatment					N = 103	N = 210			IN-313	
Follow-up										
assessments										
Data analysis and										
Manuscript										
Preparation										

#### 1.0 Introduction

Juvenile-onset fibromyalgia (JFM) is a chronic, debilitating pain condition that typically persists into adulthood for the majority of patients(1). Whereas medications offer limited and short-term symptom relief for JFM, prior research has demonstrated that cognitive-behavioral therapy (CBT) is safe, effective and durable in reducing functional disability and depressive symptoms in adolescents with this condition (2). However, 60% of patients receiving CBT did not show *clinically significant* improvement in functional disability, and pain levels remained in the moderate range despite being reduced overall (3). Objectively measured sedentary activity also did not significantly improve with CBT(4). Incorporation of a physical exercise component emerged as a logical next step to enhance CBT, yet regular participation in any physical activity has been shown to be difficult to initiate and maintain in FM patients.

Innovative features of recently developed interventions have included neuromuscular training designed to limit delayed muscle soreness as well as seamless integration with CBT to enhance psychological coping skills, decreased fear of movement as well as increased physical activity participation. Preliminary results have offered patient engagement, lack of adverse effects and very promising early results (5) indicating this treatment to have even stronger effects on disability and pain outcomes than CBT alone. The purpose of this randomized clinical trial is to test whether the FIT Teens intervention is more effective than CBT alone or graded aerobic exercise (GAE) alone and whether treatment effects are sustainable over 1-year follow-up.

#### 2.0 Study Hypotheses

#### Primary Aims

**AIM 1:** Testing the effectiveness of FIT Teens in reducing functional disability (primary outcome) compared to other treatment arms (CBT alone, GAE alone)

- H1a: The FIT Teens group will show significantly greater reduction in functional disability at 3-month follow-up compared to CBT
- **H1b**: The FIT Teens group will show significantly greater reduction in functional disability at 3-month follow-up compared to GAE

**AIM 2:** Testing whether reductions in functional disability in the FIT Teens group are maintained at lower levels than CBT alone or GAE alone over time.

- **H2a**: Functional disability in the FIT Teens group will remain significantly lower than CBT at 6-, 9- and 12-month follow-up.
- **H2b**: Functional disability in the FIT Teens group will remain significantly lower than GAE at 6-, 9- and 12-month follow-up.

**AIM 3:** Testing whether more patients who receive FIT Teens achieve clinically meaningful improvement in functional disability compared to those who receive CBT and GAE.

- **H3a**: A significantly greater proportion of the FIT Teens group will achieve clinically meaningful reduction (i.e., a decrease in at least 7.8 points) in functional disability at 3-month follow-up than CBT.
- **H3b**: A significantly greater proportion of the FIT Teens group will achieve clinically meaningful reduction (i.e., a decrease in at least 7.8 points) in functional disability at 3-month follow-up than GAE.

## Secondary Aim

**Aim 4:** To test whether the combined FIT Teens intervention is more effective in reducing pain intensity.

- **H4a**: The FIT Teens group will show significantly greater reduction in pain intensity at 3month follow-up compared to CBT.
- **H4b**: The FIT Teens group will show significantly greater reduction in pain intensity at 3month follow-up compared to GAE.
- **H4c**: Pain intensity in the FIT Teens group will remain significantly lower than CBT over time (6-, 9- and 12-month follow-up).
- **H4d**: Pain intensity in the FIT Teens group will remain significantly lower than GAE over time (6-, 9- and 12-month follow-up).

## 3.0 Study Design

This R01 study is a multi-site, 3-arm, prospective, randomized clinical trial that will test the efficacy of the FIT Teens intervention as compared with two established treatments, CBT and GAE, with respect to functional disability and pain among adolescents with fibromyalgia. After a baseline assessment, participants will be randomized in groups of 3-6 participants (defined as a "cohort") to receive a 16-session group-based intervention based on their treatment assignment (CBT, FIT or GAE). Longitudinal data will be collected at six time points (Baseline [BL], Post-Treatment [Post], 3-, 6-, 9-, and 12-months follow-up) at each of seven clinical sites (Cincinnati, OH; Columbus, OH; Hartford, CT; Boston, MA; Indianapolis, IN; Kansas City, MO; & Toronto, CA) over a 54-month period. The primary outcome of interest of this study is *functional disability*, while *pain intensity* serves as a close secondary outcome.

The COVID-19 pandemic resulted in restrictions which precluded in-person delivery of groupbased interventions; therefore a remote-delivery platform for all treatment arms was used as of July 2020. Trial included two alternate formats of treatment delivery (IP- in person) and (RD – remote delivery).

## 4.0 Power and Sample Size Estimates

(Note: the following power calculation is an amended version from the original power calculation and based on the R01 Ancillary Funded Award in February 2023 which reduced the scope of the RCT to accommodate delays due to the COVID19 pandemic)

The primary outcome for this RCT is reduction in functional disability. Power was determined for the ability to detect whether FIT Teens results in significantly greater reduction in FDI scores for Aims 1a, 1b, and 1c. Assumptions for power calculations were based on previous research showing statistically significant decreases in disability resulting from CBT (Cohen's d = .52) and GAE (Cohen's d = .40) interventions (6,7) and our pilot studies showing stronger post-treatment effect sizes for FIT Teens (d = .95 - 1.22). Power estimates were calculated with more conservative effect sizes for FIT Teens (i.e., d = .90). All power calculations were based on the assumption of 20% attrition and proper handling of missing data.

#### Aim 1b. Maintenance of treatment gains over follow-up.

Power was again calculated via the external Monte Carlo simulation capabilities in Mplus in two steps. First, 5000 dataset replications of hypothetical FDI scores were generated in a multiple group SEM format assuming: 1) standardization of FDI scores, and 2) maintained differences between the three groups at 6-, 9-, & 12-months as follows: GAE (d = 0.40), CBT (d = 0.52), & FIT (d = 0.90), and 3) N = 315 (n = 105per group) available for analysis assuming proper missing data handling. Second, the 5000 Monte Carlo replications were then analyzed using a longitudinal SEM assuming an intercept-only model (i.e., slope fixed and random effects both = 0) with dummy-coded CBT & GAE groups (FIT = reference). Results showed power > 0.80 if the standardized 'intercept on group' coefficient for either CBT or GAE is  $\beta$  > 0.38 assuming proper handling of both cluster and site nesting.

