3. STUDY DESIGN

A. Overview

The project is a 3-arm multi-site randomized clinical trial which will examine the efficacy of the new FIT Teens intervention in reducing disability in adolescents with JFM compared to CBT only or GAE only. A longitudinal design will be employed with assessments at baseline, mid-treatment, post-treatment, 3-, 6-, 9- and 12-months follow-up. We will enroll up to 420 JFM patients ages 12-17 into this trial (with at least N=105 randomized to each condition). Each treatment arm will consist of 16 in-person group-based sessions (or remote group-based sessions administered via video-platform during pandemic restrictions) held twice per week over 8 weeks. Sessions last 90 minutes and will be led jointly by a psychologist/therapist and exercise trainer using manualized protocols. Group size will vary from 4-6 JFM patients per group which has been found to be the ideal group size in our pilot work based on feedback from both trainers and patients. Parents will be included in 6 of the 16 sessions and they will receive education about the treatment and instructed in how to support the teen in their behavior change efforts outside of sessions to enhance generalizability to the home environment. After the 8-week active treatment phase, participants will return for a total of 4 group-based "booster/ maintenance" sessions (according their group assignment), or attend booster sessions via remote video sessions, at 3 month intervals through the follow-up phase in order to review their use of skills/maintenance of exercise and encourage continued practice.

The primary study endpoint is the 3-month follow-up assessment. Additional follow-ups will be conducted at 6-, 9- and 12-months post-treatment. Participants randomized after 11/22/22 will not complete the 9- or 12- month follow up or the last 2 "booster/maintenance" sessions due to a reduction in the scope of work in this project to complete the project expeditiously within the remaining timeframe and funding support.

(Protocol continued on next page)

B. Study Visit Flowchart

Participants randomized after 11/22/22 will not complete the 9- or 12-month follow up assessment (T6 and T7) or the last 2 booster sessions due to a reduction in the scope of work in this project.

C. Participants

Inclusion Criteria

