Power was again calculated via the external Monte Carlo simulation capabilities in Mplus in two steps. First, 5000 dataset replications of hypothetical FDI scores were generated in a multiple group SEM format assuming: 1.) standardization of FDI scores, 2.) maintained differences between the three groups at 6-, 9-, & 12-months as follows: GAE (d = 0.40), CBT (d = 0.52), & FIT (d = 0.90), and 3.) N = 315 randomized(n = 105 per group) available for analysis assuming proper missing data handling. Second, the 5000 Monte Carlo replications were then analyzed using a longitudinal SEM assuming an intercept-only model (i.e., slope fixed and random effects both = 0) with dummy-coded CBT & GAE groups (FIT = reference). Results showed power ≥ 0.80 if the standardized 'intercept on group' coefficient for either CBT or GAE is $\beta > 0.38$ assuming proper handling of cluster by site nesting as described above.

Aim 1c. Proportion of patients achieving clinically meaningful change.

We anticipate that the FIT Teens intervention will result in a greater proportion of patients achieving the binary outcome of clinically meaningful reduction in FDI compared to CBT and GAE. This difference is expected to be between 15%-20% based on pilot studies showing ~55% of FIT and 35-40% of CBT groups achieving clinically meaningful change. The proportion of GAE patients achieving this binary outcome is expected to be similar to CBT. Power was calculated via G*Power3 assuming 20% attrition and proper handling of missing data making n = 105 within the three arms available for analysis. Results showed power will be ≥ 0.80 for either the FIT vs. CBT or FIT vs. GAE comparison if difference between two independent proportions is at least 17% or greater (False Discovery Rate Type-1 error control will be used to evaluate results from both tests). A difference in proportion of $\geq 17\%$ between FIT Teens and CBT or GAE will provide useful information for patients and providers about the relative efficacy of the interventions.

K. Data and Safety Monitoring Plan

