#### 6.0 Statistical Analyses

Analyses will be carried out on the full intent-to-treat sample (Sample 1) as the primary analysis. Data analysis will begin with a review of all relevant variables in the dataset. For continuous variables, parametric as well as nonparametric measures of central tendency, variability, and association, will be computed. Distributional properties of potential outcomes will be evaluated and tested for normality where appropriate. Those differing markedly from normality will be considered candidates for transformation or alternative modeling techniques. Our analyses will be divided into three distinct sections. First (Primary Aims), the effectiveness of the FIT Teens intervention (Sample 2) for the reduction of functional disability will be compared with the other two treatments in several ways. FIT Teens will be compared to a CBT-only group (Sample 3) and GAE group (Sample 4) at 3-month follow-up (H1a, H1b). Additionally, differences between groups will be compared over time (i.e., 6, 9, 12-month follow-up; H2a, H2b), and analyses will be conducted to determine whether more patients in the FIT Teens intervention group obtain clinically meaningful improvement at 3-months when compared to the other two treatments (H3a, H3b).

Second, (Secondary Aims), the effectiveness of the FIT Teens intervention (Sample 2) for the reduction of pain intensity will be compared with the other two treatments (Samples 3 and 4) in several ways, similar to FDI analyses, including comparisons at 3-month follow-up (H4a, H4b), as well as whether these treatments are sustained over time (i.e., 6, 9, 12-month follow-up; H4c, H4d). Last, exploratory analyses also will be conducted to examine a mechanistic model of physical activity. Unless otherwise noted,  $\alpha = 0.05$  (two-sided) will serve as the criterion for statistical significance for all analyses. All data will be analyzed using the current version of MPlus.

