Results will be analyzed via a longitudinal GEE approach. Groups will be dummycoded with FIT as the reference class. It is hypothesized that significant and positive 'slope on group' coefficients for CBT and GAE indicating a significantly lower FDI for FIT vs. CBT & GAE. Non-independence of FDI scores will be addressed by specifying every unique combination of participant (level 2), cohort (level 3), and site (level 4) as indicators of non-independent (correlated) responses in the GEE syntax (i.e., in the 'Repeated =' syntax specification.

- **H2a** Functional disability in the FIT Teens group will remain significantly lower than CBT at 6-, 9- and 12-month follow-up.
- **H2b** Functional disability in the FIT Teens group will remain significantly lower than GAE at 6-, 9- and 12-month follow-up.

To test whether group differences on FDI scores are maintained over time, a longitudinal SEM approach will again be used. Groups will be dummy-coded with FIT as the reference class. Significant and positive 'intercept on CBT' & 'intercept on GAE' coefficients will indicate significantly lower FDI scores for FIT vs. CBT & FIT vs GAE at 6-, 9-, & 12-month assessments. Significant and positive 'slope on CBT' & 'slope on GAE' coefficients would indicate worsening FDI scores for CBT & GAE over time relative to FIT scores that have stayed the same or further improved. Nesting of clustered participants within sites will be handled with the SEM model in Mplus described above.

- **H3a** A significantly greater proportion of the FIT Teens group will achieve clinically meaningful reduction (i.e., a decrease in at least 7.8 points) in functional disability at 3-month follow-up than CBT.
- **H3b** A significantly greater proportion of the FIT Teens group will achieve clinically meaningful reduction (i.e., a decrease in at least 7.8 points) in functional disability at 3-month follow-up than GAE.

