# 6.5.1 Missing Data Planning and Analyses

Procedures are in place to minimize missing and inappropriate data (i.e., automated query resolution procedures in Medi-Data Rave®). Missing data will be handled via model-based 3-level multiple imputation in Mplus (version 8.10) as follows. Longitudinal growth curve models will be specified at level 1 (i.e. repeated measures [level 1] nested within participants [level 2]), level 2 (participants within cohorts), and at level 3 (cohorts within assessment sites). However, the effects of IV group random assignment will only be estimated within the level 1 growth curve model. The default potential scale reduction (PSR) value of 1.05 that determines convergence will be over-ridden and PSR = 1.01 will define convergence owing to model complexity.

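### The SAP's 105 per arm for maintenance (Aim 1b) ignores both the removal of 9- and 12-month visits after 11/22/22 and the 20% attrition it says it assumed

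*SAP*

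**What the plan says.** Protocol 3.A states: "Participants randomized after 11/22/22 will not complete the 9- or 12- month follow up". The same sentence drops the last two of the four booster sessions for these participants. Protocol 3.D (Maintenance Phase) and the assessment schedule in Protocol 4.A repeat the change. The 6-month visit is kept for everyone.

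The SAP does not mention the cut-off:

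- SAP 3.0 lists six data-collection time points, including 9 and 12 months, with no exception.
- SAP 2.0, 6.3 and 6.4 keep the maintenance hypotheses at all three late visits, for example "Functional disability in the FIT Teens group will remain significantly lower than GAE at 6-, 9- and 12-month follow-up". The pain hypotheses H4c and H4d follow the same pattern.
- SAP 4.0 says its power section was amended for a February 2023 award that reduced the trial's scope. It also says all power calculations assumed 20% attrition.
- SAP 4.0, Aim 1b (the maintenance hypotheses, numbered H2a and H2b elsewhere in the SAP) still assumes 105 per arm available, with "maintained differences between the three groups at 6-, 9-, & 12-months as follows". It reports: "Results showed power > 0.80 if the standardized 'intercept on group' coefficient for either CBT or GAE is" above 0.38.

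Protocol 5.J, Aim 1b, uses the same 315 (105 per arm). It calls them randomised and also "available for analysis assuming proper missing data handling". Neither document says how many participants were randomised after the cut-off.

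**The concern.** The SAP's amended power section postdates the cut-off but still counts every randomised participant as contributing at 9 and 12 months. Anyone randomised after 11/22/22 has no such visit, and 20% attrition cannot leave 105 of 105.

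Two things are at stake. First, H2 is listed among the primary aims and is worded as a claim at 6, 9 and 12 months, so readers will look at each visit. The 9- and 12-month results will rest on fewer people than the plan states, all randomised on or before the cut-off. Second, later participants were also scheduled for two boosters instead of four. The SAP does not say which maintenance schedule a 12-month result describes.

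**Working it through.** **Inputs from the documents.** Two-sided alpha 0.05 (SAP 6.0, Statistical Analyses). Standardised FDI, so SD = 1. Effects of 0.90 (FIT), 0.52 (CBT) and 0.40 (GAE), giving differences of 0.90 - 0.52 = 0.38 and 0.90 - 0.40 = 0.50. n = 105 per arm. Attrition 20%. The power model is intercept-only over 6, 9 and 12 months, so it tests one pooled level difference (all SAP 4.0).

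**Assumptions not in the documents.** f, the share randomised after 11/22/22, is 10-40% and the same in each arm. The visit correlation ρ is exchangeable, 0.5-0.9. Attrition is spread evenly. No clustering penalty is applied. The closed forms below approximate the plan's Mplus simulation.

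**Step 1: reproduce the stated figure.** For one visit, power = Φ(d·√(n/2) - 1.96). With n = 105 and d = 0.38 this is Φ(2.753 - 1.96) = 0.786. For the pooled test, information per arm is I = n[(1 - f)·3/(1 + 2ρ) + f] and power = Φ(d·√(I/2) - 1.96). At n = 105 and f = 0 it is 0.921, 0.868, 0.841 and 0.813 for ρ = 0.5, 0.7, 0.8 and 0.9. The stated value above 0.80 is therefore consistent with 105 per arm and a difference of 0.38.

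**Step 2: a 9- or 12-month FIT versus CBT comparison read alone (0.38).** n = 105(1 - f), or 105 × 0.8 × (1 - f) with attrition.

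| f | n, truncation only | Power | n, with 20% attrition | Power |
|---|---|---|---|---|
| 0 | 105 | 0.786 | 84 | 0.692 |
| 10% | 94.5 | 0.743 | 75.6 | 0.647 |
| 20% | 84 | 0.692 | 67.2 | 0.596 |
| 30% | 73.5 | 0.634 | 58.8 | 0.540 |
| 40% | 63 | 0.569 | 50.4 | 0.479 |

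For FIT versus GAE (0.50), f = 10-40% gives 0.930 to 0.801 from truncation alone and 0.867 to 0.709 with attrition.

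**Step 3: the pooled test, FIT versus CBT (0.38).** Later participants contribute one visit, the others three.

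| ρ | n = 105, f = 0 | n = 105, f = 40% | n = 84, f = 0 | n = 84, f = 40% |
|---|---|---|---|---|
| 0.5 | 0.921 | 0.881 | 0.855 | 0.802 |
| 0.7 | 0.868 | 0.840 | 0.786 | 0.752 |
| 0.8 | 0.841 | 0.821 | 0.753 | 0.730 |
| 0.9 | 0.813 | 0.803 | 0.722 | 0.711 |

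Worked example at ρ = 0.7: 3/(1 + 1.4) = 1.25. With n = 105 and f = 40%, I = 105 × (0.6 × 1.25 + 0.4) = 120.75 and power is 0.840. With n = 84 and f = 0, I = 84 × 1.25 = 105 and power is 0.786.

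At n = 105, truncation of 40% costs 1 to 4 points. Attrition alone (105 to 84, f = 0) costs 7 to 9 points. At n = 105, pooled power falls below 0.80 only when f exceeds about 0.86, 0.77 or 0.51 for ρ = 0.7, 0.8 or 0.9.

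**Step 4: the pooled test, FIT versus GAE (0.50).** At n = 84, f = 40% and ρ = 0.8, power is 0.923. It is higher at lower correlations.

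**The case against.** The strongest reply is that the stated power belongs to a pooled intercept, not to each visit. The 6-month visit is kept for everyone, so truncation removes little information. This stands. A reader might infer from the cut-off that the stated Aim 1b power has failed, but the documents do not support that: f is unknown, and at 105 per arm the pooled test stays at or above 0.80 for f up to 40% and correlation up to 0.9. Nor does truncation threaten the pooled FIT versus GAE test. H4 (pain) has no stated power to lose; only its wording at 9 and 12 months is affected.

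The reply does not cover everything. SAP 6.3 also interprets slopes over follow-up. A participant whose only maintenance visit is at 6 months gives no within-person information on that slope, so evidence of maintenance against decline comes from the earlier-randomised participants.

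The protocol allows enrolment of up to 420, so one could argue that 105 per arm is already net of attrition (315/0.8 ≈ 394 randomised). But Protocol 5.J, Aim 1b, calls the 315 randomised, and the timeline in Protocol 7 also shows 315.

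A reader might also infer that the SAP wrongly imputes visits that never existed. SAP 6.5.1 says only "Missing data will be handled via model-based 3-level multiple imputation in Mplus" and is silent on unscheduled visits. Absence fixed by randomisation date is by design, and imputing under missing-at-random is defensible. It adds no information about months 9 and 12, but it is not an error in itself.

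Finally, restricting the late contrasts to earlier participants has a price. It departs from the full intent-to-treat sample, discards later participants' earlier data from those contrasts, and gives more weight to in-person delivery.

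**Conclusion.** The point holds as an inconsistency between protocol and SAP, with a sample size the design does not deliver. The figure of 105 per arm at 6, 9 and 12 months equals the number randomised. It cannot hold at 9 and 12 months if anyone was randomised after 11/22/22, and it is not net of the 20% attrition that SAP 4.0 says was assumed.

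The material loss is in FIT versus CBT at 9 or 12 months read alone: 0.74 to 0.57 from truncation, or 0.65 to 0.48 with attrition, against 0.79 at 105. For the pooled test truncation is minor and attrition is the larger problem (0.786 at 84 per arm and ρ = 0.7, then 0.752 with f = 40%). Pooled FIT versus GAE stays at about 0.92 or more for correlations up to 0.8.

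These figures rest on the assumed f, the assumed visit correlation and no clustering penalty. The 3-month primary endpoint is not touched by the truncation.

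**What to change.** - Reconcile SAP 2.0, 3.0, 4.0, 6.3 and 6.4 with the 11/22/22 cut-off.
- Report the number randomised after it, by arm.
- Restate Aim 1b size and power for each visit and for the pooled test, net of attrition.
- Treat the 9- and 12-month visits of later participants as not scheduled, not as dropout, and say in SAP 6.5.1 how the model handles them.
- State that the 9- and 12-month results rest on data from participants randomised on or before the cut-off, and which maintenance schedule they describe. Report an analysis limited to those participants, at least as a sensitivity analysis. Use everyone at 6 months.

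The cost is SAP wording, one recalculation and a less favourable power figure. No new data are needed.
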